### Start Date of New Anticancer Therapy:

Start dates for follow-up anticancer therapy, radiotherapy (where applicable), and surgical procedures (where applicable) will be temporarily imputed in order to define duration of response. Dates will only be imputed when a month and year are available but the day is missing. The imputed date(s) will not be stored on the anticancer therapy, radiotherapy, or surgical procedure datasets. The following rules will be used to impute the date when partial start dates are present on anticancer therapy radiotherapy, and/or surgical procedures dataset[s]:

Dataset	Date	Missing Element	Rule
Anticancer Therapy Where applicable: Radiotherapy	Start Date	day, month, and year	
 
No Imputation for completely missing dates
 

		day, month	
 
No imputation for missing day and month (note the eCRF should only allow for missing day)
 

		day	
 
If partial date falls in the same year and month as the last dose of study treatment, then assign to earlier of (date of last dose of study treatment+1, last day of month).
 
If partial date falls in the same year and month as the subject's last assessment and the subject's last assessment is PD, then assign to earlier of (date of PD+1, last day of month).
 
If both rules above apply, then assign to latest of the 2 dates
 

Dataset	Date	Missing Element	Rule
			
 
Otherwise, impute missing day to the first of the month.
 

	End Date		
 
No imputation for partial end dates will be performed
 

The date of new anticancer therapy is derived as the earliest date of new anticancer therapy (e.g., chemotherapy), radiotherapy (where applicable), or cancer related surgical procedure (where applicable) and will include imputed dates. If the date of new anticancer therapy is an imputed date, then the date of new anticancer therapy flag variable is assigned the value of 'D' to indicate that the day portion of the date is imputed (following ADaM convention).

As multiple dates are used to derive the date of new anticancer therapy ensure that the date of new anticancer therapy flag is only set to 'D' if the derived date is imputed. For example if the date of new radiotherapy is imputed but the date of new anticancer therapy is prior to date of new radiotherapy and the new anticancer therapy date is not a partial date then the flag should be set to missing as the date used for the new anticancer therapy is not an imputed date.

#### **10.2.6. Imputation of Missing Exposure End Dates**

Missing exposure end date will not be imputed.

#### **10.2.7. Baseline Definition**

Baseline will be defined as the most recent, non-missing value prior to or on the first study treatment dose date (this can be either GSK 3174998 or pembrolizumab). For laboratory data, baseline will be defined as the most recent, non-missing value from a central laboratory prior to or on the first study treatment dose date. If there are no central labs collected for a subject and lab test prior to or on the first dose of study treatment, the most recent, non-missing value from a local laboratory prior to or on the first dose of study treatment will be defined as the baseline value.

If the latest pre-dose value is collected on the day of treatment, the time of treatment will be used to identify the baseline value. If the pre-dose time point value is identified as baseline, and the data is recorded in triplicate the average will be used.

For subjects who did not receive study treatment during the study, baseline will be defined as the latest, non-missing collected value.

#### **10.2.8. Change from baseline**

Change from baseline will be presented for safety data as described in [Section 13](#).

Change from baseline is calculated as:

- For records occurring after baseline: (visit value) – baseline value.

Percent change from baseline is calculated as:

- For records occurring after baseline: (change from baseline / baseline value) \* 100

Unless otherwise stated, if either the baseline or visit value is missing, the change from baseline and/or percent change from baseline is set to missing as well.

### **10.2.9. Multiple Assessments**

All data will be reported according to the nominal visit date for which it was reported (that is, no visit windows will be applied during dataset creation). Unscheduled data will only be included in the display sections that report worst-case. For summaries that collapse data across multiple planned time intervals, the worst-case data at each collapsed interval will be selected.

If multiple assessments on different days are reported for the same scheduled assessment, then the latest assessment for that scheduled assessment will be analyzed.

If multiple assessments are reported on the same date for the same scheduled planned time, then the worst-case result will be analyzed, with the exception of laboratory data reported from both central and local laboratories.

Furthermore, as quantitative ECG values will be measured in triplicate: 3 assessments are collected for each scheduled planned time, the first 3 measures will be used to compute the mean values for ECG intervals at each scheduled planned time.

For vital signs, three readings of blood pressure (BP) and pulse rate will be taken and the first reading will be discarded. The second and third readings will be averaged and recorded on eCRF to give the measurement reported at each time point.

Data from all assessments (scheduled and unscheduled), including multiple assessments, will be included in listings.

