6.3.1.4. Dose Delay

GSK3174998 ± pembrolizumab may be interrupted for situations other than treatment-related AEs such as medical / surgical events or logistical reasons not related to study therapy. Subjects should be placed back on study therapy within 3 weeks of the scheduled interruption, unless otherwise discussed with the Sponsor. The reason for interruption should be documented in the patient's study record.

If there is a dose delay between 1 and 49 days (2 dosing cycles + 7 days), the procedures at the original scheduled visit (including dosing) should be performed as soon as possible. All subsequent visits will follow a Q3W calendar schedule. Subjects with infusion delays causing 2 consecutive missed doses due to toxicity should discontinue study drug(s) unless the treating investigator and Sponsor/Medical Monitor agree there is strong evidence supporting continued treatment. While no washout from study treatments is required for subjects requiring elective surgery or palliative radiation therapy while on study, investigators and site staff are encouraged to schedule these procedures to fall in between dosing days (see Section 6.10.1. for details on permitted medications and non-drug therapies).

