GSK3174998 Pharmacokinetics (1 mL)	Pre EOI+30m EOI+4h	EOI+24h ^d	X	X	Pre EOI+30m EOI+4h	EOI+24 ^d	X	X	Pre EOI+30m	Pre EOI+30m	Pre EOI+30m	Pre EOI+30m	Pre ^e	X	X	
Part 2 only: Pembrolizumab Pharmacokinetics (3 mL)	Pre EOPI+30m	EOI+24h	X	X	Pre					Pre		Pre	Pre ^e	X	X	
Anti- GSK3174998 antibodies ^{c,f} (4 mL)	Pre				Pre				Pre	Pre	Pre	Pre	Pre ^e	X	X ^f	
Part 2 only: Anti-Pembrolizumab antibodies ^{c,f} (6 mL)	Pre				Pre					Pre		Pre	Pre ^e	X	X ^f	

Timepoint Definitions:

X = Anytime during visit

Pre = within 60 min before the start of the GSK3174998 infusion

EOI+30m = within 30 minutes of the end of the GSK 3174998 infusion

EOPI+30m = within 30 minutes of the end of the pembrolizumab infusion

EOI +4h = within 4 hours \pm 10 minutes of the end of the GSK3174998 infusion

EOI+24h = 24 hours \pm 4 hours after the end of the GSK3174998 infusion

- a. Informed consent for optional pharmacogenetics research must be obtained before collecting a sample. It is recommended that the blood sample be taken at the first opportunity after a subject has met all eligibility requirements, and can be done up to 28 days before Day 1.
- b. If the baseline/pre-dose sample is not viable, samples for PBMCs are not needed at subsequent visits.
- c. In addition to these scheduled immunogenicity assessments, "event-driven" testing will also be employed for those subjects that experience anaphylaxis, serious hypersensitivity, or AEs related to study drug administration that led to withdrawal from the study. See Section 9.4.2.4 for full details.
- d. Day 2 PK samples are only required during the dose-escalation phases of the study.
- e. Dose 8 and every 4 dosing cycles
- f. In the event of a hypersensitivity reaction that is either 1) clinically-significant in the opinion of the investigator, or 2) leads to the subject withdrawing from the study, blood samples should be taken from the subject for immunogenicity testing at the time of the event and again 30 days, 12 weeks, and 24 weeks after.
- g. If the EOI+4h RO sample is scheduled to be collected after the last lab courier pick-up time of the day, the sample should be collected as late as possible to enable processing and shipping on the same day as collection.
- h. If a tumor biopsy is taken at the time of PD, then a plasma sample should also be collected for cfDNA + exosomes,
- i. Receptor Occupancy and phenotyping panels will only be collected in Parts 1A and 2A of the study

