## 15.1. Drug Concentration Measures

PK analysis of GSK3174998 and pembrolizumab drug concentration-time data will be conducted by non-compartmental methods under the direction of CPMS, Quantitative Sciences, GSK or Merck.

Drug concentration-time data will be listed for each subject and summarized by descriptive statistics at each time point by cohort.

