## **16. PHARMACODYNAMIC AND BIOMARKERS ANALYSES**

### **16.1. Pharmacodynamic and Biomarker Analyses**

Receptor occupancy data will be summarized and plotted.

Other biomarker data may be reported separately from the main clinical study report, generated by GSK biomarker team if applicable. All endpoints of interest from all

comparisons will be descriptively and/or graphically summarized as appropriate to the data.

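### Pre-dose samples taken before a delayed dose are summarised at their nominal visit with no window, so partly washed-out values enter the concentration and receptor-occupancy summaries

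*SAP*

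**What the plan says.** Protocol 6.3.1.4 (Dose Delay) sets the rule for a late dose: "If there is a dose delay between 1 and 49 days (2 dosing cycles + 7 days), the procedures at the original scheduled visit" are to be done, together with the dose itself, as soon as possible. It then adds: "All subsequent visits will follow a Q3W calendar schedule".

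The notes to Table 14 in Protocol 7.1 define the pre-dose time point by the infusion and not by the calendar: "Pre = within 60 min before the start of the GSK3174998 infusion". After Day 1, pre-dose GSK3174998 concentration is scheduled on Days 22, 43, 64, 85 and 106 and at later doses. Pre-dose receptor occupancy is scheduled on Days 22 and 43 only, and only in Parts 1A and 2A.

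SAP 10.2.9 assigns visits as follows: "All data will be reported according to the nominal visit date for which it was reported (that is, no visit windows will be applied". It also says: "If multiple assessments on different days are reported for the same scheduled assessment, then the latest assessment for that scheduled assessment will be analyzed".

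SAP 15.1 has concentrations "summarized by descriptive statistics at each time point by cohort". SAP 16.1 says only: "Receptor occupancy data will be summarized and plotted". Neither gives a timing rule.

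Two provisions come close to a safeguard. SAP 9 drops from PK and occupancy analysis any subject who received different doses, but is silent on late doses. SAP 15.2 bases non-compartmental parameters on actual sampling times, but that does not reach the concentration-by-time-point or occupancy summaries.

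**The concern.** A pre-dose value at Day 22 is naturally read as the level three weeks after dose 1. If dose 2 is late, so is the sample, and the drug has had longer to clear. The SAP reports the value under the same label as on-time samples. Early dosing is limited to 72 hours (Protocol 6.1), while late dosing can run to weeks, so the errors fall mostly on the low side and do not cancel.

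The latest-assessment rule can make this worse. If an on-time sample was drawn, the dose held and the sample repeated at the delayed infusion, the later value is the one analysed.

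At stake is how the study report describes end-of-interval exposure and target engagement by dose level, in cohorts small enough for one late value to move a mean.

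**Working it through.** **The plan's own figures.** The outer limit of the delay rule is two cycles plus 7 days: 2 × 21 + 7 = 49 days, as stated. Protocol 4.5.1 also reproduces: 0.003 mg/kg × 70 kg / 3 L = 0.07 µg/mL. Predicted occupancy is 0.07/(1.45 + 0.07) = 4.6% (stated as 5%) and 0.07/(0.2 + 0.07) = 26% (stated as 26%).

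**Effect on one sample.** Protocol 4.5.1 expects a half-life longer than 2 weeks; 14 to 21 days is my assumed range, with log-linear decline. The ratio of a sample delayed by d days to the on-time value is 2^(−d/half-life).

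| Delay | Days since previous dose | Half-life 14 d | Half-life 21 d |
|---|---|---|---|
| 7 d | 28 | 0.71 | 0.79 |
| 21 d | 42 | 0.35 | 0.50 |
| 49 d (by exception) | 70 | 0.09 | 0.20 |

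**Effect on a cohort mean.** Suppose n subjects have otherwise equal values and one has ratio r. The arithmetic mean is multiplied by (n − 1 + r)/n and the geometric mean by r^(1/n). For one 21-day delay (r = 0.354 or 0.50):

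- n = 4: arithmetic −16% or −12.5%; geometric −23% or −16%.
- n = 6: arithmetic −11% or −8%; geometric −16% or −11%.
- n = 12: arithmetic −5% or −4%; geometric −8% or −6%.

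These sizes match the design: up to 4 subjects initially, 3 to 6 in most escalation cohorts and at most 12 per dose level (Protocol 4.1.1 to 4.1.3).

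**Effect on occupancy (illustration only).** This applies the protocol's equation, C/(EC50 + C), to end-of-interval concentrations with a 14-day half-life. At 0.1 mg/kg the starting concentration is 0.1 × 70/3 = 2.33 µg/mL. That falls to 0.825 at 21 days and 0.292 at 42 days.

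- EC50 1.45: 0.825/2.275 = 36% on time; 0.292/1.742 = 17% after a 21-day delay.
- EC50 0.2: 0.825/1.025 = 80% on time; 0.292/0.492 = 59% after a 21-day delay.

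At 10 mg/kg with EC50 1.45 the change is only from 98% to 95%. The same delay therefore matters much more at low doses.

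**What the protocol's windows allow.** With ±3 days at each of two consecutive visits, compliant doses lie between 21 − 6 = 15 and 21 + 6 = 27 days apart. A 7-day delay after an on-time dose gives 28 days, just outside. At 27 days the ratio is 2^(−6/14) = 0.74 to 2^(−6/21) = 0.82, so limiting the summaries to this range removes the large distortions but not all spread.

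**The case against.** Several objections stand in part.

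- **The 49-day limit.** A reader might infer that Day 22 values from Day 71 are to be expected. The documents do not support that. Protocol 6.3.1.4 expects a return within 3 weeks for interruptions other than treatment-related events, unless discussed with the sponsor. Protocol 5.4.1 expects discontinuation after a toxicity delay of more than 3 weeks, unless continuation is agreed. Longer delays are exceptions. Protocol 6.3.1.4 also uses two consecutive missed doses as a toxicity limit, so the two sections must be reconciled. The problem is already present at 21 days.
- **The Cmin endpoint.** A reader might infer that this secondary endpoint is biased. Both abbreviation lists define Cmin as the minimum observed concentration, and a low value that was observed does not understate that. Derived parameters use actual times. What remains open is whether Ctau is read at 21 days or at the delayed sample; SAP 15.2 does not say.
- **The expansion dose.** A reader might infer that the case for 0.3 mg/kg is undermined. That dose was chosen before this SAP, and the expansion cohorts had closed. Late samples lower apparent occupancy, so they could not create a false finding of saturation.
- **Clustering of delays by dose.** This is possible but not shown. Protocol 4.5.3 reports no apparent dose relationship for adverse events.
- **The visit label.** The protocol does not say how the eCRF names a delayed visit, and SAP 10.2 leaves derivation detail to dataset specifications that are not in these documents. Still, performing the original visit's procedures most naturally means recording them under that visit, and no text says otherwise.
- **Descriptive use only.** No formal PK analysis is planned, concentrations are listed by subject, and a median would move less than a mean. This limits the harm but does not correct the tables.

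**Conclusion.** The point holds for the descriptive summaries. As written, the plan puts partly washed-out values into the by-time-point concentration summaries and into the Day 22 and Day 43 pre-dose occupancy summaries of Parts 1A and 2A, with no rule to find or separate them. Per sample, the value is 0.71 to 0.79 of the on-time level after 7 days and 0.35 to 0.50 after 21 days. This rests on log-linear decline, a half-life of 14 to 21 days and the delayed sample keeping its original visit label. The number of delayed doses is not given, so the overall bias cannot be sized. The documents do not support extending the point to Cmin as they define it or to the choice of expansion dose. It is worth correcting because the cohorts are small, the error runs mainly one way and the times needed are already recorded.

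**What to change.** In SAP 15.1, 15.2 and 16.1:

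- Derive the actual time since the previous infusion for each pre-dose PK and receptor-occupancy sample.
- Flag samples outside 15 to 27 days, the interval the protocol's ±3-day windows allow, and leave them out of the nominal-time summaries. A rule of 21 ± 3 days would be too tight, because it would drop samples from two consecutive compliant doses.
- Show the all-samples summary as a sensitivity display.
- Keep flagged samples in the listings and in plots against actual time since last dose.
- State that Ctau refers to 21 days after dose.

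Separately, reconcile Protocol 5.4.1 and 6.3.1.4 on the limit for delays.

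The cost is SAP wording and one derived variable. PK sample times and infusion times are already captured (Protocol 7.5.1 and 6.1), and the infusion time dates any pre-dose occupancy sample to within an hour. The downside is that a few values leave the main descriptive tables. If delays follow toxicity, that could introduce some selection, which the all-samples display would show.

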### **10.2.10. Actual Treatment**

The actual treatment of a subject will be derived from exposure data. The first dose the subject received is used as actual treatment.

### **10.2.11. Extended Loss to Follow-up or Extended Time without an Adequate Assessment**

If [two] or more scheduled disease assessments are missed and are then followed by an assessment of PD or death, PFS will be censored at the last adequate assessment prior to PD or death. As scheduled disease assessment is every 12 weeks, a window of 175 days (24 weeks + 7 day window) will be used to determine whether there was an extended time without adequate assessment. That is, if the time difference between PD/death and

last adequate assessment is more than 175 days, then PFS will be censored at the last adequate assessment prior to PD/death.

### 10.2.12. Date Associated with Response

For each disease assessment after baseline, a date will be associated with the response based on collective group of disease assessments made within the protocol visit window. For complete response (CR) and partial response (PR), this will be assigned to the latest date within the disease assessments. For stable disease (SD), Non-CR/Non-PD or Not Evaluable, this will be assigned to the earliest date within the disease assessments. For progressive disease (PD), assign to the earliest assessment date associated with the progression. Dates associated with irRECIST response values will be handled similarly.

## 10.3. Values of Potential Clinical Importance

### 10.3.1. Laboratory Parameters

Reference ranges for all laboratory parameters collected throughout the study are provided by the laboratory. A laboratory value that is outside the reference range is considered either high abnormal (value above the upper limit of the reference range) or low abnormal (value below the lower limit of the reference range). The laboratory reference ranges will be provided on the listings of laboratory data. Clinical laboratory test results outside of the reference range will be flagged in the listings.

Laboratory grades will be reported, where applicable, using the Common Terminology Criteria for Adverse Events (CTCAE v4.0).

### 10.3.2. ECG Parameters

The following criteria will be used to flag electrocardiogram (ECG) values that are values of potential clinical importance:

To identify QTc (Fridericia's) values of potential clinical importance, NCI-CTCAE v4.0 will be used to assign grades (see adverse event 'Electrocardiogram QT corrected interval prolonged'). Note that there is a slight inconsistency between NCI-CTCAE v4.0 and ICH E14 (Absolute QTc interval prolongation). It was decided to align with NCI-CTCAE v4.0 for the oncology standard categories.

ECG Parameter	Potential Clinical Importance (PCI) Range	Unit
Absolute QTcF interval	>450 to <481 (Grade 1) ≥481 to <501 (Grade 2) ≥501 (Grade 3)	msec
Increase from baseline QTcF	Increase of ≥31 to ≤60 Increase of >60	msec

The following criteria will be used to flag some ECG values that are values of potential clinical importance:

ECG Parameter	Potential Clinical Importance (PCI) Range	Unit
PR interval	<110 (L) and >220 (H)	msec
QRS interval	<75 (L) and >110 (H)	msec

Averages (rounded to the integer) are the basis of analyses when time point data is collected in triplicate.

### 10.3.3. Vital Signs

To identify heart rate values of potential clinical importance, NCI-CTCAE v4.0 will be used to assign categories that align with the grades for ‘Sinus bradycardia’, ‘Sinus tachycardia’, ‘Supraventricular tachycardia’, and ‘Ventricular tachycardia’.

The following criteria will be used to flag vital sign values (based on the averaged value) that are values of potential clinical importance:

Vital Sign Parameter	Potential Clinical Importance (PCI) Range	Unit
Decrease from baseline Heart Rate	Decrease to <60	bpm
Increase from baseline Heart Rate	Increase to >100	bpm

To identify blood pressure values of potential clinical importance, NCI-CTCAE v4.0 will be used to assign categories that align with the grades for ‘Hypertension’.

Vital Sign Parameter	Potential Clinical Importance (PCI) Range	Unit
Increase from baseline Systolic Blood Pressure	Increase to $\geq 120$ to <140 (Grade 1) Increase to $\geq 140$ to <160 (Grade 2) Increase to $\geq 160$ (Grade 3)	mmHg
Increase from baseline Diastolic Blood Pressure	Increase to $\geq 80$ to <90 (Grade 1) Increase to $\geq 90$ to <100 (Grade 2) Increase to $\geq 100$ (Grade 3)	mmHg

Systolic blood pressure below 120 and diastolic blood pressure below 80 are considered as normal range and will receive Grade 0 designations.

To identify temperature values of potential clinical importance, NCI-CTCAE v4.0 will be used to assign categories that align with the grades for ‘Hypothermia’ and ‘Fever’.

Vital Sign Parameter	Potential Clinical Importance (PCI) Range	Unit
Increase from baseline temperature	Increase to $\geq 38$	Degrees C
Decrease from baseline temperature	Decrease to $\leq 35$	Degrees C

Additionally, temperature and heart rate will be further categorized for reporting based on the following:

- Heart rate (beats/min): <60, 60-100, and >100; and
- Temperature (°C):  $\leq 35$ ,  $35 < 38$ ,  $\geq 38$ .

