Infusion reactions are a well-documented AE associated with the administration of mAbs. Infusion reactions typically develop within 30 minutes to 2 hours after initiation of drug infusion, although symptoms may be delayed for up to 48 hours. The incidence of infusion reactions varies by mAb agent, and there are multiple mechanisms known to lead to infusion-related reactions including both IgE-dependant anaphylactic and non-IgE dependent anaphylactoid hypersensitivities. Cytokine release syndrome, and when severe, cytokine “storm”, has been identified as a sequelae of the immune system activation associated with infusion reactions.

Infusion reactions may affect any organ system in the body. Most are mild in severity, although severe and even fatal reactions occur. As a group, infusion reactions (including both cytokine mediated and allergic) usually occur during or within a few hours of drug infusion. Occasionally, a reaction may occur one to two days after administration. The NCI-CTCAE (version 4.0) for grading adverse reactions during chemotherapy administration has a scale for grading the severity of infusion reactions and separate grading scales for allergic reactions and anaphylaxis. While use of these separate grading scales may be useful for classifying the nature of an infusion reaction for research purposes, they are less useful for clinical care, since it may not be obvious if the subject is having an allergic infusion reaction or a non allergic infusion reaction.

Clinically, infusion reaction may present with flushing, itching, urticaria, and/or angioedema, repetitive cough, sudden nasal congestion, shortness of breath, chest tightness, wheeze, sensation of throat closure or choking, and/or change in voice quality, faintness, tachycardia (or less often bradycardia), hypotension, hypertension and/or loss of consciousness, nausea, vomiting, abdominal cramping, and/or diarrhea, sense of impending doom, tunnel vision, dizziness, and/or seizure, severe back, chest, and pelvic pain.

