9.4.1.5. Other Safety Measures

Data for vital signs and ECGs will be summarized based on pre-determined criteria identified to be of potential clinical concern. Further details will be provided in the RAP.

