### 13.8.1. Vital Signs

Values of vital signs will be listed. The categories defined in [Section 10.3.3](#) will be flagged in listings.

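### SAP 10.3.3 categorises blood pressure only upward and labels everything below 120/80 as normal range, and SAP 13.8.1 lists vital signs without the summaries that the protocol promises

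*SAP*

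**What the plan says.** **Categories (SAP 10.3.3).** The blood pressure rule opens: "To identify blood pressure values of potential clinical importance, NCI-CTCAE v4.0 will be used to assign categories that align with the grades for ‘Hypertension". Both of its rows run upward ("Increase from baseline Systolic Blood Pressure" and the matching diastolic row), with Grades 1 to 3 starting at 120 mmHg systolic and 80 mmHg diastolic. It closes: "Systolic blood pressure below 120 and diastolic blood pressure below 80 are considered as normal range and will receive Grade 0 designations". In the same section heart rate has a low-side row ("Decrease from baseline Heart Rate", to under 60 bpm), and temperature has one at 35 °C or below.

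**Display (SAP 13.8.1).** "Values of vital signs will be listed", with the 10.3.3 categories flagged in that listing. No table is specified.

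**What the protocol promised.** Protocol 9.4.1.1 names vital signs among the serial safety endpoints to be summarised by nominal visit and by worst case on treatment. Protocol 9.4.1.5 adds: "Data for vital signs and ECGs will be summarized based on pre-determined criteria identified to be of potential clinical concern". Protocol 9.4 requires departures from its analysis plan to be documented in the reporting and analysis plan (that is, the SAP) and in the study report.

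**Why low pressure is relevant.** Protocol Table 7 lists hypersensitivity reaction and severe cytokine release as potential risks. Protocol 6.3.1.3 includes among the presenting signs of an infusion reaction "faintness, tachycardia (or less often bradycardia), hypotension, hypertension and/or loss of consciousness".

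**The concern.** Changes in vital signs are one of the examples named in the primary safety endpoint of both parts. The plan has only one blood pressure scale, and it points away from the direction that matters for a drug whose stated risks include infusion reaction and cytokine release. Someone scanning the listing for flags would find raised readings marked, and low readings unmarked in a band called normal. With no table, a pattern of lower pressures at some dose levels would have to be found by reading individual values. The protocol had committed to showing this in summary form.

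**Working it through.** No sample size, power or error rate bears on this point. The check applies the stated rule to readings and then counts the planned displays.

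**Step 1: apply the 10.3.3 rule.** The readings below are my illustrations, not trial data.

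| Reading (mmHg) | Category under SAP 10.3.3 | Flagged? |
|---|---|---|
| 118/78 | Grade 0 | No |
| 100/60 | Grade 0 | No |
| 85/50 | Grade 0 | No |
| 70/40 | Grade 0 | No |
| 75/45, fallen from 150/95 | Grade 0; not an increase | No |
| 125/70, systolic risen from baseline | Systolic Grade 1 | Yes |

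The Grade 0 band has no floor, so the rule cannot separate 118/78 from 70/40.

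**Step 2: compare with the other parameters.** Heart rate is flagged below 60 and above 100 bpm, and temperature at 35 °C or below and at 38 °C or above (SAP 10.3.3). PR is flagged below 110 and above 220 msec, and QRS below 75 and above 110 msec (SAP 10.3.2). SAP 10.3.3 also gives low, middle and high reporting bands for heart rate and temperature, and none for blood pressure. The one-sidedness is therefore not a general convention of these sections.

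**Step 3: count the displays.** I looked at each place where the SAP could specify a vital-sign table.

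- 10.2.8 defers change from baseline to Section 13, and Section 13 gives none for vital signs.
- 10.2.9 admits unscheduled data to worst-case displays and to listings; no worst-case vital-sign display is planned.
- 13.8 has a general sentence on denominators at scheduled visits but specifies no table.
- 13.8.1 gives one listing with flags.

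The result is one listing and no summary table. Laboratory data (13.7), performance status (13.8.2) and ECG (13.8.3) all have summaries.

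**Step 4: see what other routes capture.** Appendix 8 of the protocol makes an abnormal vital sign an adverse event if the investigator judges it clinically significant. Appendix 11 makes infusion reactions, anaphylaxis and cytokine release syndrome events of special interest at any grade. SAP 13.2 and 13.3 tabulate both. What remains uncovered is a low measured pressure that was not reported as an event.

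**Step 5: population affected.** Protocol 2.3.5 gives 45 subjects on monotherapy and 96 on the combination, with 3 in both: 45 + 96 − 3 = 138 subjects at the 13 August 2019 cut-off. The number with low readings is not given, so the gap cannot be sized further.

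**The case against.** The best defence is context. The Grade 0 sentence closes a block about hypertension, so on that scale it means only not hypertensive, and nothing in the SAP carries the grade into a conclusion about low pressure. That stands, and it rules out reading the plan as analysing hypotension as a normal outcome. It does not rescue the words normal range, because no other blood pressure scale exists in the plan.

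Three stronger inferences are tempting, and the documents do not support them.

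- *That hypotension in an infusion reaction disappears.* It does not: the adverse-event and special-interest tables cover it once it is reported.
- *That readings taken during a reaction are dropped.* SAP 9 and 10.2.9 put all scheduled and unscheduled assessments in the listings.
- *That the report could not show whether pressure fell with dose or with added pembrolizumab.* The listed values can be read by dose, since SAP 9 bases safety listings on actual treatment. A contrast with and without pembrolizumab was never planned: the study is non-randomised, and SAP 8 states that there are no treatment comparisons.

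It is also fair to say that a by-visit table would add little on infusion reactions. Table 13 of the protocol sets no fixed post-infusion vital-sign times, and its footnote c makes the readings pre-dose from week 12 onward. The worst-case table with unscheduled readings is the one that would inform that risk. The by-visit table is still owed, because the protocol promised it. Finally, vital signs are one example within a broad descriptive safety endpoint with no hypothesis test, so no inference is biased.

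**Conclusion.** The point holds as a one-directional categorisation with a misleading label, together with an undocumented departure from the protocol's promised summaries. The protocol left further detail to the analysis plan, but dropping the summary is more than detail. The consequence is confined to the flagging and tabulation of measured low blood pressure not reported as an adverse event; raw values and reported events are preserved. This assumes that the SAP is followed as written and that no vital-sign table is specified elsewhere, for example in programming specifications outside these documents. It is worth correcting because it concerns a named component of the primary safety endpoint and a recognised sign of a listed risk.

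A secondary inconsistency is that SAP 10.2.9 says "three readings of blood pressure (BP) and pulse rate will be taken and the first reading will be discarded", with the other two averaged and the average recorded. Current Protocol 7.4.4 asks for no replicate readings. The protocol's change log shows the replicate instruction deleted at Amendment 2 (16 August 2016), and it reports six subjects already enrolled at the 17 May 2016 cut-off. Some early values may therefore be averages. This is stale text that probably leaves the analysed values unchanged.

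**What to change.** - **SAP 10.3.3:** reword Grade 0 as 'no hypertension' in place of the reference to a normal range. Deleting the sentence outright would leave such readings without a grade on that scale. Add a low-side, decrease-from-baseline display category for systolic and for diastolic pressure, matching the treatment of heart rate and temperature. The documents give no cut-offs, so the sponsor should set them. They are display flags, not management rules.
- **SAP 13.8.1:** add vital-sign summaries by nominal visit and by worst post-baseline value, by dose level or expansion cohort, using the 10.3.3 categories. Include unscheduled readings in the worst-case table. If the sponsor prefers to keep a listing only, record that as a departure under Protocol 9.4, with the reason.
- **SAP 10.2.9:** reconcile the three-reading text with Protocol 7.4.4, noting that subjects enrolled before Amendment 2 may have averaged values.

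The cost is SAP wording, a few flag definitions and a small set of tables from data already collected. The downside is that some isolated low readings of no clinical meaning will be flagged.
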